further mitigate potential risks associated with dosing, enrolled participants are titrated to their assigned dose (15 mg/kg over 1 dose, 40 mg/kg over 2 doses, or 60 mg/kg over 3 doses). Amyloid-related imaging abnormality – edema (ARIA-E) and amyloid-related imaging abnormality – hemosiderin deposits (ARIA-H) have been observed in Study AL002-2, with 3 cases associated with serious and severe symptoms. Because the serious and severe symptomatic cases were in participants with an apolipoprotein E epsilon4/epsilon4 (APOE e4/e4) genotype (APOE e4/e4) genotype, participants with this genotype are no longer participating in this trial. For additional information regarding these cohorts, please refer to Section 5 of the IB.

AL002-LTE is an extension of the ongoing AL002-2 study for all participants who have completed the planned treatment period, who are medically stable, and who consent to dosing for an additional 49 weeks. Participants who received active treatment in the parent study will remain on their current dose in the AL002-LTE study, and participants who received placebo in the parent study will be titrated to [REDACTED] mg/kg as described in Section 5.1. AL002 will be administered to study participants and all procedures related to the study will be performed by qualified persons at investigational sites from the parent study (ie, AL002-2). The Investigator, the study staff at the site, study participants, participant study partners, and the clinical site monitors will remain blinded to the dose of AL002 participants are receiving throughout the AL002-LTE study as well as which study drug (AL002 vs. placebo) and dose they received in the AL002-2 study.

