2. STUDY OBJECTIVES AND ENDPOINTS

The study objectives and endpoints are provided in [Table 2-1](#).

Table 2-1. Study Objectives, Endpoints and Estimands for LTE

| Primary Objectives | Primary Safety Endpoints and Primary Estimand |
|--|---|
| 
To evaluate the long-term safety and tolerability of AL002 in participants with AD.
 | 
Part 1: Primary Safety Endpoint and Estimand:
 
 • Treatment condition: Group T-T (AL002 15 mg/kg, 40 mg/kg or 60 mg/kg IV Q4W) continues their Core Study treatment in the LTE Study; Group P-TC treated with Placebo in the Core study will be titrated to 60 mg/kg of AL002 in the LTE study. • Target population: adult participants with AD excluding apolipoprotein E (APOE) epsilon 4 (e4)-homozygous (e4/e4) participants. • Primary endpoints: AESI incidence and SAE incidence over all weeks. • Accounting for intercurrent events: a composite strategy will be used to handle intercurrent events as below: 
 ○ Hypothetical strategy for handling premature study drug discontinuation for any reason (AEs with a start date more than 90 days after study drug discontinuation are not counted) ○ Treatment policy strategy for handling all other intercurrent events. • Population-level summaries: the descriptive statistical summaries for each treatment group of incidence rates for all AESIs and SAEs over similar periods of time. 
Part 2: Primary Safety Endpoints:
 
 • Changes from baseline (CFBs) in vital signs, physical findings, neurological findings, ophthalmological findings, ECG findings, and clinical laboratory results. • MRI abnormalities (ARIA events) • C-SSRS. 
Primary Estimand for Safety Endpoints Above:
 
The estimand for the Part 2 endpoints is defined with similar attributes as for the Part 1 estimand except applied to the different endpoints
 |

| Primary Objectives | Primary Safety Endpoints and Primary Estimand |
|--|---|

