| To evaluate the effect of dose titration on ARIA in participants with AD | 
Part 3: Primary Endpoints:
 
 • Incidence and severity of ARIA in participants undergoing titration 
Primary Estimand for Incidence and Severity of ARIA:
 
The estimand for incidence and severity is defined with similar attributes as for the Part 1 primary estimand except that it is applied to incidence and severity of ARIA, and difference in incidence of ARIA events between slower and faster titration groups will be reported
 |
| Secondary Objective | Secondary Endpoints |
| To evaluate the PK of AL002 in participants with early AD | 
 • Serum PK concentrations of AL002 and relevant PK parameters. |
| To evaluate the effects of AL002 with COAs in participants with AD | 
LTE Efficacy Endpoints:
 
 • Disease progression as measured by the CFB in CDR-SB score. • CFB in MMSE score. • CFB in RBANS score. • CFB in ADAS-Cog13 score. • CFB in ADCS-ADL-MCI score. • CFB in ADCOMS. • CFB in modified iADRS. 
Main Estimand for Efficacy:
 
The main estimand for the LTE Efficacy endpoints is defined with similar attributes as for the primary safety estimand in Part 1 except the following.
 
 • Accounting for intercurrent events: a composite strategy will be used to handle intercurrent events as below: 
 ○ Hypothetical strategy for handling premature study drug discontinuation for any reason (data will be considered missing after early discontinuation of study drug plus 37 days). ○ Treatment policy strategy for handling all other intercurrent events. • Population-level summary: the percent reduction relative to placebo decline (the proportional treatment effect), comparing each dose level to placebo. |

| Primary Objectives | Primary Safety Endpoints and Primary Estimand |
|--|--|
| Exploratory Objectives | Exploratory Endpoints |

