3. STUDY DESIGN

3.1 Study Design

This is a Phase 2, LTE study of participants with AD. The study will enroll participants who completed the planned treatment period in AL002-2 (Core Study). Study sites are located in North America, Australia, Europe, and Argentina.

Participants who were randomized to active treatment in the Core Study will remain on their previously assigned dose. Participants who were previously on placebo in the Core Study will be assigned to the Titration Cohort (TC), which will initiate with a starting dose of either 2 mg/kg or 6 mg/kg that will be increased over 32 weeks or 24 weeks, respectively, to reach the target dose of 60 mg/kg per the Titration Algorithm (for details of the Titration Algorithm, refer to the Study Protocol).

The planned duration of the LTE study is 56 weeks, and LTE study treatment extends from LTE Day 1 to Week 48. Dosing duration may be extended beyond this time through a protocol amendment, within the context of emerging favorable safety data. AL002 will be administered via IV infusion at the study site on Day 1 (after all necessary baseline assessments have been completed) and will be repeated subsequently once every 4 weeks throughout the treatment period.

The first dose of the AL002-LTE should be within the 4-week window (± 5 days) of the last dose of the Core Study, to maintain continuity of study treatment. Delays of the first AL002-LTE dose beyond that window will constitute protocol deviations.

Dosing for any individual participant may be stopped, paused, or reduced based on emerging safety data and/or the development of ARIA-E or ARIA-H. If a participant discontinues the study prior to the end of their planned treatment period, they will need to return for an Early Termination (ET) Visit and that will mark the end of their participation in the study.

At study entry and throughout the treatment period, safety will be assessed through monitoring of AEs (including AESIs and SAEs), changes in laboratory and vital sign values, incidence of findings from physical, neurological, ECG, MRI, ophthalmological exams, and reports of suicidal ideation or behavior. Serum PK will be assessed for investigation of exposure-response and exposure-safety relationships. Blood samples for assessment of ADA will be taken throughout the study.

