3.5 Sample Size

It is expected that 80% to 90% of the participants who completed the planned treatment period in the Core Study and are not APOE e4/e4 will enroll in the LTE Study. Currently, there are 220 such participants in the Core Study who either completed planned treatment or are ongoing, so 176 to 198 participants are expected.

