All of the MRI summaries described above will also be provided separately for participants with the following APOE genotype(s) (1) e4 carriers (including e2/e4, e3/e4 and e4/e4), and (2) non-e4 carriers (excluding e2/e4, e3/e4 and e4/e4).

For Integrated Analysis, all summaries described in this section will be provided for events across two studies as defined in Section 7.4.1.2. For LTE Analysis, only the overall summary of ARIA will be provided for events during the LTE Study.

For Integrated Analysis, the difference in proportion of participants with ARIA-E events between a slower titration rate over 48 weeks and a faster titration rate over 48 weeks will be estimated by the Cochran-Mantel-Haenszel (CMH) method adjusting for the APOE e4 status. The faster titration rate will be represented by data from the AL002 60 mg/kg treatment group during the first 48 weeks of the Core Study among participants who were on dose titration (i.e., received the first dose on or after July 22, 2021 in the Core Study) and had at least one evaluable post-baseline MRI scan. The slower titration rate will be represented by data from the first 48 weeks of the LTE Study, among Titration Cohort participants who had at least one evaluable post-baseline MRI scan in the LTE Study. Both 90% and 95% CIs for the difference in the ARIA-E events and p-value will be reported from the CMH method. The same analysis will be repeated for ARIA-H.

The statistical tests (the CMH method) of ARIA events between the slower and faster titration groups will not be performed at the first IA at the time of unblinding of the Core Study due to limited data from the LTE study at this IA, but will be performed in all analyses after the first IA.

In the Integrated Analysis, the Kaplan-Meier curves for the time to the first occurrence of ARIA-E during both the Core and LTE Studies will be plotted. For participants who experienced at least one ARIA-E, the time to the first occurrence of ARIA-E is the time from the first dose date to the onset date of the first ARIA-E occurrence. For participants who did not experience ARIA-E, the censor date will be the earlier date of the last MRI scan date, any death date, and the last dose date plus 90 days. Similarly, the Kaplan-Meier curves for the time to the first occurrence of ARIA-H will be plotted.

All MRI findings will be listed.

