8. ANALYSES TO BE PERFORMED AT INTERIM

In general, analyses outlined in this SAP apply to the final analysis, when the LTE study concludes.

The scope of the first IA at the time of unblinding of the Core Study is specified in Section 8.1.

The scope of the subsequent IAs will be the same (Section 8.1), except that the inferential statistical analysis (Section 7.6.2) will be performed when there is sufficient data at the data cutoff date of the IA.

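### Interim ARIA comparison of slow against fast titration counts part-followed Titration Cohort participants as ARIA-free over 48 weeks, so it can favour slow titration when the 48-week risks are equal

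*SAP*

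**What the plan says.** SAP Section 7.4.8 plans a CMH estimate, adjusted for APOE e4 status, of the difference in ARIA-E proportions between the two titration speeds, each over 48 weeks. It reports 90% and 95% confidence intervals and a p-value, and repeats the analysis for ARIA-H.

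- **Fast arm:** titrated 60 mg/kg participants in their first 48 weeks of the Core Study.
- **Slow arm:** the first 48 LTE weeks "among Titration Cohort participants who had at least one evaluable post-baseline MRI scan in the LTE Study".
- **Timing:** the test is skipped at the first interim because LTE data are limited, and then "will be performed in all analyses after the first IA".
- **Sufficient-data condition:** Section 8 keeps the same scope for later interims, except that "the inferential statistical analysis (Section 7.6.2) will be performed when there is sufficient data at the data cutoff date of the IA". Section 7.6.2 holds the efficacy models, not the ARIA test. Section 8.1.3 keeps the Section 7.4.8 ARIA summaries in interim scope.
- **Estimand:** the Part 1 summary in Table 2-1 is of "incidence rates for all AESIs and SAEs over similar periods of time". For Part 3, the ARIA objective, "The estimand for incidence and severity is defined with similar attributes as for the Part 1 primary estimand".
- **Titration:** SAP Section 3.1 says the Titration Cohort dose "will be increased over 32 weeks or 24 weeks, respectively, to reach the target dose of 60 mg/kg". Protocol Section 1.2.2 gives the parent-study titration as "15 mg/kg over 1 dose, 40 mg/kg over 2 doses, or 60 mg/kg over 3 doses".
- **Entry to the LTE:** SAP Section 3.5 says "there are 220 such participants in the Core Study who either completed planned treatment or are ongoing".

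**The concern.** One evaluable scan admits a participant to a 48-week proportion. The LTE Week 8 window in Table 7-13 covers days 2 to 85, so one clean scan there puts a participant in the denominator as a non-event for the full 48 weeks. Participants who have already had ARIA count as events; the miscounted ones are those who are part-followed and have not had ARIA so far.

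The arms differ in maturity. The comparator's window lies inside a Core Study that doses for up to 96 weeks and is already unblinded at the first interim. LTE entry is staggered. Because the Titration Cohort needs 24 or 32 weeks to reach 60 mg/kg, short follow-up can miss the target-dose period altogether.

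With equal 48-week risk, this can only lower the slow arm's expected count. At stake are the interim difference, intervals and p-value for a primary objective, which could show fewer ARIA events only because that arm was watched for less time. It also departs from the comparable-periods attribute that the ARIA estimand takes over from Part 1.

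**Working it through.** **The plan's figure.** SAP Section 3.5: 0.80 × 220 = 176 and 0.90 × 220 = 198, as stated. With four equal arms this is 176/4 = 44 to 198/4 = 49.5 per arm. The ARIA rates, group sizes and power for this test are redacted in Protocol Section 8.1, so the values below are assumptions.

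**Expected bias, ignoring scan dates.** Let *p* be the 48-week risk in both arms, *F(f)* the share of 48-week events that have occurred by week *f*, and *f* the follow-up at cutoff. Then bias = *p* × (E[*F*(min(*f*, 48))] − 1). Take *f* uniform on 8 to 48 weeks.

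- Half the events in the first 24 weeks, so *F* = *f*/48: E[*F*] = 28/48 = 0.583. Bias is 0.20 × (−0.417) = −8.3 points at *p* = 20%, and −12.5 points at *p* = 30%.
- 80% of events in the first 24 weeks: E[*F*] = 0.4 × 0.533 + 0.6 × 0.9 = 0.753. Bias is −4.9 points at 20%, and −7.4 points at 30%.

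A simulation of the stratified CMH test (4,000 runs per scenario, 40 or 60 per arm, 60% e4 carriers, two-sided 0.05) agrees. The ranges below are for the same onset timing in both arms.

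| Slow-arm follow-up | Mean difference (points) | Significant in favour of slow |
|---|---|---|
| All 48 weeks | about 0 | 2.1% to 2.8% |
| Half at 48, half uniform 8–48 | −2.3 to −6.3 | 4.4% to 11.4% |
| Uniform 8–48 | −4.8 to −12.6 | 8.5% to 36.4% |
| Uniform 8–32 | −7.3 to −17.8 | 13.6% to 67.5% |

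**With the planned scan weeks.** Core scans are at Weeks 2, 4, 6, 8, 12, 24 and 48 (Table 7-12). LTE scans inside 48 weeks are at Weeks 8, 16, 24, 32 and 40 (Table 7-13). Assumptions: 45 slow and 50 fast; 60% carriers; 48-week risk 35% in carriers and 15% in non-carriers, so 0.6 × 35% + 0.4 × 15% = 27% overall. An event counts at the first scan after onset if that scan is within follow-up and within 48 weeks. There were 3,000 trials per scenario. Cells give bias in points / false positives favouring slow (nominal 2.5%).

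| Follow-up | (a) constant hazard | (b) 60% of events by Week 8 | (c) fast early, slow delayed to Weeks 16–40 |
|---|---|---|---|
| 8–48 weeks | −12.5 / 32% | −6.6 / 11% | −16.1 / 52% |
| 16–64 weeks | −8.2 / 16% | −4.1 / 7% | −9.1 / 19% |
| 32–56 weeks | −5.1 / 8% | −2.9 / 5% | −2.9 / 5% |
| All at 48 weeks | −3.9 / 5.5% | −2.0 / 3.8% | −0.2 / 2.2% |

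The last row is not a follow-up effect. It arises because the Core Study has a Week 48 scan and the LTE has none between Weeks 40 and 56. Subtracting it leaves the part due to short follow-up: −8.6, −4.6 and −15.9 points at 8–48 weeks; −4.3, −2.1 and −8.9 at 16–64; −1.2, −0.9 and −2.7 at 32–56.

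**Sensitivity.** With risks of 25% and 8% at 8–48 weeks, false positives are 22%, 8% and 34%. Arm sizes from 35/35 to 50/60 with carrier share 45% to 75% give 26% to 35% for (a) and 9% to 13% for (b). Independent repeats of the 8–48 week case gave 32–33%, 10–11% and 53–55%.

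**After the fix.** At 16–64 weeks, (64 − 48)/(64 − 16) = 1/3 of the Titration Cohort qualifies, or 15 of 45. False positives fall to 4.2%, 2.9% and 2.0%.

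**The case against.** **The cohort may be nearly mature by any later interim.** Section 7.4.8 implies that Core dosing began before 22 July 2021. A participant dosed then would enter the LTE about 96 + 4 = 100 weeks later, near June 2023, roughly 70 weeks before the SAP was signed on 25 October 2024. Core starters up to about December 2021 would already have 48 LTE weeks at signature. With follow-up assumed at 24 to 96 weeks, false positives were 10%, 5% and 5%, against 8%, 4% and 3% with everyone at 48 weeks in the same approximate set-up. This weakens the 8–48 week case. It does not remove the problem: the placebo visit windows in Section 7.1.1.2 are cut at LTE Day 1 from about Core Week 48 onwards, so later Core starters could enter with short follow-up. A spread of 8 to 96 weeks still gives 14%, 7% and 13%.

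**Pattern (c) is not a case of no effect.** It assumes that slow titration delays onset. That stands. Only the 48-week risk is equal in (c), but that risk is what the test claims to compare. Patterns (a) and (b) show the bias without any delay. Protocol Section 1.4 reports early onset for anti-amyloid trials, which points towards the smaller figures in (b).

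**The test may not be unconditional.** Sections 7.6.2 and 7.7.3 carry the same unconditional sentence for the efficacy and biomarker models, yet Section 8 makes Section 7.6.2 depend on sufficient data. The wording is therefore loose. Even so, the only text specific to the ARIA test requires it, and no passage makes it conditional.

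**The consequence is limited.** No stated decision rule uses the p-value, the number and dates of later interims are not given, and censored Kaplan-Meier curves are already planned. All true. But the curves are only plotted and do not correct the reported difference, intervals or p-value.

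**Conclusion.** The concern holds. Followed as written, Section 7.4.8 gives a biased interim difference whenever a later interim falls before the Titration Cohort has been followed through the window. The direction follows from the text. The size rests on assumed risks, arm sizes, onset patterns and cutoff dates: several points and a several-fold excess of false positives if much of the cohort is early in follow-up, and only 1 to 3 points beyond the scan-schedule remainder at 32 to 56 weeks. If no interim after the first precedes full follow-up, the cutoff causes no bias. The likely harm is a misleading interim result on a primary safety objective, not a wrong final conclusion. It should be corrected before any interim that runs the test; confidence in its practical size is medium.

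**What to change.** 1. At interims, run the CMH test only on Titration Cohort participants whose first LTE dose was at least 48 weeks before the data cutoff. Select by time since first dose, not by ARIA status or scan completion. If fewer than a pre-stated number qualify, defer the test to the final analysis. A 40-week rule would keep more people, but the LTE Week 40 scan window runs to Day 337, so 48 weeks is the safer limit.
2. Extend the sufficient-data condition in Section 8 to Section 7.4.8.
3. Also report an APOE-stratified Kaplan-Meier cumulative-incidence difference from first AL002 dose (Mantel-Haenszel weights, the censoring rule already in Section 7.4.8), as an estimate with its interval and no p-value. In the 8–48 week case its Week 48 value is −3.9, −2.3 and 0.0 points for (a), (b) and (c), against −12.5, −6.6 and −16.1 for the CMH difference.
   - Week 24 is scanned in both studies and can be read earlier, labelled as a reading during titration. It gives 0.1 and 0.0 for (a) and (b) but −11.6 for (c), so it cannot stand in for the 48-week result.
   - Read Week 48 only once participants have been followed to LTE Week 40, and note that this is the last scheduled LTE scan inside the window.
   - Avoid a log-rank p-value, because the scan weeks differ between the studies.

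Items 1 and 2 are the core; item 3 supplements them. The cost is SAP wording and one program, with no new data. Interim tests use fewer people (15 of 45 at 16–64 weeks, and none at 8–48 weeks, where the test is deferred), and intervals are somewhat wider.

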7.4.9 Ophthalmological Examinations

Incidence of any post-baseline treatment-emergent PCS ophthalmological examinations findings as indicated on the Optical Coherence Tomography, Visual Acuity, Slit Lamp Exam, and Fundoscopy electronic CRFs will be summarized for each visit (refer to Table 7-14 and Table 7-15 for analysis visit window definitions), and overall during the treatment period. For overall, the record with the most severe finding will be selected for a participant. PCS ophthalmological examinations findings are defined as

- On the Optical Coherence Tomography electronic CRF

- Percent CFB in left eye retinal central subfield thickness (in micrometers) $\geq 20\%$,
- Percent CFB in right eye retinal central subfield thickness (in micrometers) $\geq 20\%$,
- Percent CFB in left eye subfoveal choroidal thickness (in micrometers) $\geq 20\%$,
- Percent CFB in right eye subfoveal choroidal thickness (in micrometers) $\geq 20\%$.
- On the Visual Acuity electronic CRF
 - Left eye best-corrected visual acuity worsen 3 categories since baseline (the higher the best-corrected visual acuity, the worse):
 - 20/32 and 20/30 are pooled and are considered one category,
 - When counting, 3 categories do not include the baseline assessment but include the post-baseline assessment, e.g., from 20/20 at baseline to 20/40 at a post-baseline, it is counted as worsen 3 categories.
 - Right eye best-corrected visual acuity worsen 3 categories since baseline.
- On the Slit Lamp Exam electronic CRF
 - Left Anterior Cell Score by SUN Criteria ≥ 0.5 (the higher the Anterior Cell Score, the worse),
 - Right Anterior Cell Score by SUN Criteria ≥ 0.5 .
- On the Fundoscopy electronic CRF
 - Left eye results shown as abnormal (clinically significant),
 - Right eye results shown as abnormal (clinically significant),
 - Left eye results shown as abnormal (not clinically significant),
 - Right eye results shown as abnormal (not clinically significant).

All ophthalmological examinations findings will be listed separately by electronic CRF.

7.4.10 Neurological Examinations

Incidence of any post-baseline treatment-emergent PCS neurological examinations findings as indicated on the Neurological Exam electronic CRF will be summarized for each visit (refer to [Table 7-16](#) and [Table 7-17](#) for analysis visit window definitions) and overall during treatment periods. For overall, the record with the most severe finding will be selected for a participant. Shift tables from baseline to post-baseline will be provided.

All neurological examinations findings will be listed.

7.4.11 Physical Examinations (PE)

All PE findings will be listed.

7.4.12 Other Safety Assessments

7.4.12.1 Pregnancy Test

Reproductive status and pregnancy test results at any visit will be listed.

